6.4.4 Laboratory safety assessment

Daily tests for hemoglobin, complete blood count including platelet count, serum creatinine, AST, ALT, INR, cardiac Troponin I on Day 1, Day 2, and Day 3.

For blood volume see Section 7.1.

6.4.5 Physical examination

Daily physical examination will be performed on Day 1, Day2, Day 3 and until discharge. Final examination on day 30 (follow-up visit)

6.4.6 ECG

6.4.6.1 Resting 12-lead ECG

On Day 1 and Day 2. Furthermore, whenever it is considered appropriate according to symptoms and physical findings. Particular inspection for bradycardia, conduction disturbances, ventricular pauses.

6.4.6.2 Real time monitoring

Will be only applied during the coronary angiography and the PCI procedure, unless patient status dictates further monitoring or CCU admission, depending on the investigator's judgement.

6.4.7 Vital signs

Daily physical examination with vital signs (heart rate, blood pressure) will be performed on Day 1, Day2, Day 3 and until discharge. Final examination with vital signs (heart rate, blood pressure) on day 30 (follow-up visit)

6.4.8 Other safety assessments

During physical examination after antiplatelet initiation and after PCI, physical examination will be specifically guided to include assessment of symptoms and signs indicative of general or access site bleeding

6.5 Patient reported outcomes (PRO)

Chest pain severity during balloon occlusion at the time of PCI will be reported by the patients during the post-PCI assessment according a numerical 10 point scale (0: no pain, 10: most severe discomfort ever experienced)

7. BIOLOGICAL SAMPLING PROCEDURES

All laboratory parameters will be determined in a local laboratory according to standard clinical practice. No additional tests will be performed on the patients enrolled in the study,

apart from the ones performed as standard clinical practice on patients with stable CAD or NSTEMI-ACS undergoing coronary angiography and PCI

7.1 Volume of blood

According to local clinical practice, approximately 8 ml of blood will be drawn each time for laboratory testing

7.2 Handling, storage and destruction of biological samples

All biological samples will be handled according to local standard clinical practice. No storage of biological samples will be performed.

7.3 Labeling and shipment of biohazard samples

Not applicable.

7.4 Chain of custody of biological samples

Not applicable.

7.5 Withdrawal of informed consent for donated biological samples

Not applicable

8. ETHICAL AND REGULATORY REQUIREMENTS

8.1 Ethical conduct of the study

The procedures set out in this protocol, pertaining to the conduct, evaluation, and documentation of this study, are designed to ensure that the Sponsor and investigator abide by Good Clinical Practice Guidelines and under the guiding principles detailed in the declaration of Helsinki. The study will also be carried out in keeping with applicable local laws and regulations. This may include an inspection by the Sponsor representatives and/or Regulatory Authority representatives at any time. The investigator must agree to the inspection of study-related records by the Regulatory Authority/Sponsor representatives, and must allow direct access to source documents to the Regulatory Authority/ Sponsor representatives.

Modifications to the study protocol will not be implemented by either the Sponsor or the investigator without agreement by both parties. However, the investigator may implement a deviation form, or a change of, the protocol to eliminate an immediate hazard to the trial subjects without prior EC/IRB/Sponsor approval/favorable opinion. As soon as possible, the implemented deviation or change, the reasons for it and if appropriate the proposed protocol amendment should be submitted to the EC/IRB/Sponsor. Any deviations from the protocol must be fully explained and documented by the investigator.

8.2 Ethics and regulatory review

Documented approval from appropriate EC(s)/IRBs will be obtained for all participating centers prior to study start, according to GCP, local laws, regulations, and organizations. When necessary, an extension, amendment, or renewal of the Ethics Committee approval must be obtained and also forwarded to the Sponsor. The Ethics Committees must supply to the Sponsor, upon request, a list of the Ethics Committee members involved in the vote and a

statement to confirm that the Ethics Committee is organized and operates according to GCP and applicable laws and regulations.

Regulatory Authority approvals/ authorizations/ notifications, where required, must be in place and fully documented prior to study start

8.3 Informed consent

A core information and Informed Consent Form will be provided. Prior to the beginning of the study, the investigator must have the ECs/IRB written approval/ favorable opinion of the written Informed Consent Form (ICF) and any other written information to be provided to subjects. The written approval of the EC/ IRB together with the approved subject information/ ICFs together with the approved subject information/ICFs must be filed in the study files.

Written informed consent must be obtained before any study specific procedure taken place. Participation in the study and date of informed consent given by the subject should be documented appropriately in the subject's files.

8.4 Changes to the protocol and informed consent form

No protocol, informed consent process, or informed consent document may be modified without prior approval from the IRB unless it is necessary to eliminate an apparent and immediate hazard to one or more of the participants. Such modifications consist of revisions of or amendments to existing study documents. Any planned modification must be submitted to the IRB for review and approval before being implemented or used with participants

8.5 Audits and inspections

Monitoring and auditing procedures defined/ agreed by the Sponsor will be followed, in order to comply with Good Clinical Practice (GCP) guidelines. The center will be visited at regular intervals by a monitor to ensure compliance with the study protocol, GCP and legal aspects. This will include on-site checking of the case report forms (CRF) for completeness and clarity, cross-checking with source documents, and clarification of administrative matters.

9. STUDY MANAGEMENT

9.1 Training of study site personnel

Investigators involved in this study must not enroll any patient prior to completion of a formal meeting conducted by the Clinical Research Associate designated by the Sponsor. This meeting will include an inventory of study supplies, a detailed review of the protocol and CRF, training on study procedures and other procedures required of GCP. Investigators who are not GCP certified will undergo GCP training during the study.

9.2 Monitoring of the study

9.2.1 Source data

The investigator must maintain adequate and accurate records to document the conduct of the study and substantiate the study data. These documents comprise Essential Documents Source Documents. Source documents are original hospital records, clinical charts, subject screening checklist, original laboratory reports, pharmacy dispensing records, recorded data from

automated instruments, transcriptions certified after verification as being accurate, electronic media, subjects' files, and records kept at the pharmacy, at the laboratories and at medicolegal departments involved in the study.

The investigator must maintain source documents for each patient in the study. All information on CRFs must be traceable to these source documents.

9.3 Study timetable and end of study

Contract execution to IRB/EC Approval	6 months
IRB/EC approval to first subject In	1 month
First subject in to 50% enrollment	6 months
50% enrollment to last subject in	6 months
Last subject in to last subject last visit	1 month
Last subject last visit to completion of final study report	3 months
Last subject last visit to abstract submission	4 months
Last subject last visit to manuscript submission	6 months

10. DATA MANAGEMENT

Data collection and recording will be performed through paper case report forms (pCRFs) that will be provided by the Sponsor to the participating site for each subject separately. The use of a waterproof ballpoint black pen is recommended for the record of data on the pCRF.

The Principal Investigator must review the CRFs for completeness and accuracy and must sign and date the appropriate CRF page. All CRFs must be filled out legibly.

Corrections to the data on the CRFs must only be made by drawing a straight line through the incorrect data and by writing the correct value/data next to the information that has been crossed out. Corrections must only be performed by the Principal Investigator or his qualified designees. Each correction must be initialed and dated by the Principal Investigator or his/her authorized staff.

Erasures of incorrect data with the use of correction fluid or tape are not allowed.

The monitor of the study will review and check all CRFs, for accuracy (including source data verification) and completeness and subsequently the Investigator shall correct all forms with missing information and/or incorrect entries. Every documentation inserted on the CRF, corrections and other changes shall be performed exclusively by the responsible Investigator or the authorized by the Investigator person.

With the exception of the evident errors, all corrections must be accompanied with explanatory comments.

Clinical data will be managed by appropriate Data-management staff, who will be responsible for constructing a database containing all previously described data for the purpose of data analysis. The data-management staff will perform checks of data consistency and completeness. The data review will permit the generation of queries for the clarification of unclear/ missing/ inconsistent data. The errors found will be assessed by the Data Manager of the study and investigators will be involved in resolving them. All changes to the database will be recorded in an audit trail file. If a change is necessary once the investigator has no further access to the database, a query will be sent to the investigator for confirmation of the change. The investigator's signature is requested to demonstrate approval of the change that was made.

The investigator will be responsible for retaining all records pertaining to the study as specified in the appropriate contract.

At the end of the study, a copy of all data-sets will be provided to the Sponsor on electronic support. A study report will be written at the end of the study. Information on the study results will be given to the Regulatory Authorities, within required times, as indicated by local regulations.

11. EVALUATION AND CALCULATION OF VARIABLES

11.1 Calculation or derivation of efficacy variable(s)

The primary efficacy variable, cardiac troponin I at 24 hours post-PCI will be determined according to local standard clinical practice. In detail, cTnI will be analyzed with an automated immunoassay (Bayer ADVIA IMS Troponin-I Ultra method, Bayer, Berlin, Germany). The 99th percentile of the cTnI level in a reference population (upper reference, limit, URL) of healthy volunteers was below the lower limit of detection of 0.04 ng/mL. The coefficient of variation (CV) of the assay was <10%, complying with the recommendations of the European Society of Cardiology (ESC)/ American College of Cardiology (ACC)/ American Heart Association (AHA) for optimal precision. The analytical range was 0.01 to 50ng/mL, with an assay sensitivity of 0.006 ng/mL.

Chest pain during PCI is a secondary efficacy variable. It will be assessed during the post-PCI clinical examination of the subject by the investigator or by an appropriately qualified person to whom the investigator has delegated this duty. A numerical 10 point scale will be used (0: no pain, 10: most severe discomfort ever experienced).

ST-segment deviation during balloon occlusion will be monitored as a secondary efficacy variable. It will be defined as the absolute value of ST-segment deviation at 60-80ms after the J-point in mm at the beginning of coronary angiography minus ST-segment deviation at 60-80ms after the J-point in mm during balloon occlusion.

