5.3 Blinding and procedures for unblinding the study

The TRIP study will be an open label study with a blinded assessor. Accordingly, two investigators unaware of the patients' allocation will assess outcomes. In detail, each study patient will have a post-procedural cTnI measurement and a pain measurement not amenable to assessment; however the ST-segment deviation will be decided by two blinded expert investigators. In the event of discrepant assessments, final outcome will be defined by consensus between the two assessors.

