12.2 Methods of statistical analyses

The efficacy analysis will be performed in the population of subjects valid for safety analysis.

The statistical assessment of the primary outcome measure (post-procedural cTnI) will be performed using ANCOVA (analysis of covariance), with post-procedural cTnI as a dependent variable, -ticagrelor/clopidogrel treatment and –RIPC/no RIPC as fixed factors and pre-procedural cTnI as a covariate. If not mentioned otherwise, all statistical tests will be performed tow-sided with a type I error rate of 5% and 95% confidence intervals (two-sided) will be given.

The statistical assessment of the secondary outcome measures (pain score, and ST-segment deviation) will be performed using ANOVA (analysis of variance). The ANOVA tests the null hypothesis that samples in two or more groups are drawn from populations with the same mean values. If the ANOVA test is statistically significant, pairwise comparison of subgroups will be performed with the Tukey-Kramer test. If not mentioned otherwise, all statistical tests will be performed tow-sided with a type I error rate of 5% and 95% confidence intervals (two-sided) will be given.

The safety analysis will be performed in the population of subjects valid for safety analysis.

The incidence of the composite of major and non-major bleeding according to the TIMI criteria and the incidence of major bleeding will be tabulated and further analyzed using Fisher's exact test. Fisher's exact test is a significance test for a 2x2 table. This test evaluates all distribution probabilities for a 2 x 2 table and produces an exact probability for a given set of observed frequencies. The null hypothesis is that the row and column variables are unrelated, or that there is no difference in the respective proportions. If not mentioned otherwise, all statistical tests will be performed two-sided with a type I error rate of 5% and 95% confidence intervals (two-sided) will be given.

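### Chest pain, a tested secondary outcome in an open-label trial, is collected by staff who need not be unaware of allocation, so it is open to avoidable collector influence that the assessor-blind label does not cover.

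*Combined protocol and SAP*

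**What the plan says.** Sections 3.1 and 5.1.1 call the trial assessor-blind. Section 5.3 is more specific: "The TRIP study will be an open label study with a blinded assessor". It says that two investigators unaware of allocation assess outcomes, and then narrows this. On the primary outcome and pain it reads "each study patient will have a post-procedural cTnI measurement and a pain measurement not amenable to assessment". The other secondary outcome is treated differently, in the words "however the ST-segment deviation will be decided by two blinded expert investigators". Of the efficacy outcomes, only ST-segment deviation goes to the blinded pair.

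On collection, section 11.1 states: "It will be assessed during the post-PCI clinical examination of the subject by the investigator or by an appropriately qualified person". Sections 6.2 and 6.3.1 say the same. None of the three sets a condition on what that person may know about allocation.

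Section 6.5 classes the score as a patient-reported outcome: "Chest pain severity during balloon occlusion at the time of PCI will be reported by the patients during the post-PCI assessment". The scale is described as numerical in sections 2.2, 6.2, 6.5 and 11.1, and as analog in 6.3.1.

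On status and analysis, section 11.1 says "Chest pain during PCI is a secondary efficacy variable", and section 12.2 says "The statistical assessment of the secondary outcome measures (pain score, and ST-segment deviation) will be performed using ANOVA", at a two-sided 5% level, with Tukey-Kramer pairwise comparisons if the ANOVA is significant.

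**The concern.** The cTnI value comes from an automated immunoassay and does not depend on who writes it down. A pain rating given to a member of staff at a clinical examination can depend on how the question is put, what is said around it, and how a hesitant answer is recorded. If that person knows the drug, the RIPC allocation and the study hypothesis, a small systematic difference between groups can arise that has nothing to do with treatment. It enters the treatment comparisons directly, and no analysis of the collected data can separate it from a real effect. It could produce a false difference or hide a true one.

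At stake is how far one of the trial's two secondary efficacy results can be trusted, and whether a reader of the assessor-blind label would wrongly suppose that it protects this outcome.

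**Working it through.** **What the plan protects, outcome by outcome**

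| Outcome | How obtained | Blinding safeguard stated |
|---|---|---|
| cTnI at 24 h (primary) | Automated immunoassay (6.3.1, 11.1) | Not adjudicated (5.3) |
| ST-segment deviation (secondary) | Read by two experts (5.3) | Both unaware of allocation; consensus if they differ |
| Chest pain (secondary) | Reported by the patient, collected by the investigator or a delegate (6.2, 6.3.1, 6.5, 11.1) | None at collection; not adjudicated (5.3) |

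Pain is the only efficacy outcome that is both subjective and without a stated safeguard.

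**The plan's own figure**

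The documents give no SD, expected difference or power for pain. The only sample size is for cTnI (12.3), and one route reproduces it:
- Adjusted SD = 0.20 × √(1 − 0.7²) = 0.1428.
- Ticagrelor main effect = (0.12 + 0.24)/2 − (0.08 + 0.14)/2 = 0.07.
- n per drug level = 2 × (0.1428 × (1.960 + 0.842)/0.07)² = 65.4, so 66, or 33 per group.
- 33 × 1.15 = 37.95, so 38 per group and 152 in total.

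Nothing in this depends on pain. Its only use here is the evaluable number: 152 × 0.85 = 129.

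**Illustration of the effect of a collection shift**

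Inputs: N = 129; two-sided 5% level (12.2); pain SD of 2, 2.5 or 3 points (assumed); no true effect; an average difference b of 0.25 or 0.5 point between the two levels of one factor, due to collection alone (assumed).

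Section 12.2 describes a comparison of means across groups followed by Tukey-Kramer, which fits a four-group omnibus F test. With equal groups, two of the four means lie b/2 above the overall mean and two lie b/2 below it. The non-centrality is therefore

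λ = N × (b/2)² / SD²,

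with 3 and 125 degrees of freedom and a 5% critical value of 2.68. For example, b = 0.5 and SD = 2 give λ = 129 × 0.0625/4 = 2.02.

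| SD | b = 0.25: λ | False-positive rate | b = 0.5: λ | False-positive rate |
|---|---|---|---|---|
| 2 | 0.50 | 8.0% | 2.02 | 18.9% |
| 2.5 | 0.32 | 6.9% | 1.29 | 13.4% |
| 3 | 0.22 | 6.3% | 0.90 | 10.6% |

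The nominal rate is 5%. A single-factor main-effect test on the same inputs would be more sensitive to such a shift (about 16-29% at 0.5 point, 8-11% at 0.25), but section 12.2 does not describe that test for pain.

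**The case against.** The best defence starts from section 6.5: pain is already a patient-reported outcome, so the rating is the patient's and not the investigator's. The clause in 5.3 then reads naturally as saying that neither an assay value nor a patient's own rating can be re-read afterwards by two experts, whereas an ST tracing can. On that reading 5.3 openly discloses that pain lies outside the blinded assessment. The delegation wording also permits a collector who is unaware of allocation. Much of this stands.

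It also rules out several stronger readings that a reader might infer:

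- *That the investigator asks for the score verbally and prompts the patient.* The documents do not say whether the patient speaks, points or marks a form. The mode of administration is unspecified. Influence is possible, but not shown.
- *That the protocol treats pain as being as objective as cTnI.* It names the two in one clause about assessment and makes no claim about objectivity.
- *That the collector is necessarily an unblinded investigator.* That is one permitted case; a delegate's knowledge of allocation is not specified.
- *That self-completion would remove the bias.* It removes only the collector's part. Patients know their drug. Whether they know their RIPC status is unclear, because section 5.1.1 describes the comparator as no RIPC and section 12.1.1 describes a sham procedure.
- *That the false-positive rate would reach 16-29%.* This needs the main-effect test, and both the shift and the SD are assumed in any case.

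What the defence does not answer is that no safeguard is required at the point of collection. That pain cannot be adjudicated later is a reason to protect how it is collected. A patient-reported score can still be influenced by the member of staff who obtains and records it.

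**Conclusion.** The concern holds in a limited form. A patient-reported, formally tested secondary outcome is collected in an open-label trial with no requirement that the collector be unaware of allocation, and the assessor-blind description does not extend to it. This is a weakness in design that is cheap to reduce, not evidence that bias will occur.

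Its size cannot be established from the documents. The illustrated rise from 5% to about 11-19% (0.5-point shift) or about 6-8% (0.25-point shift) rests on an assumed SD of 2 to 3 points, 129 evaluable patients, no true effect and the four-group ANOVA. It shows that a modest shift could matter and that a small one would change little. The primary endpoint and the sample size are untouched.

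**What to change.** - **Sections 6.2, 6.3.1, 6.5 and 11.1:** have the patient mark a printed 0-10 numerical scale with fixed wording at the start of the post-PCI assessment, and transcribe the mark unchanged to the CRF. Where a patient needs help, use an existing delegate unaware of allocation if one is available. Describe the scale as numerical throughout, replacing the analog wording in 6.3.1.
- **Section 5.3:** replace the clause on pain with a statement that pain is self-reported by the patient and is not adjudicated by the blinded assessors. Simply deleting the clause would be a mistake, because the remaining text would imply that the blinded pair assess pain.
- **Remaining limitation:** state that bias from patients' own knowledge of allocation remains, and reconcile no RIPC (5.1.1) with the sham procedure (12.1.1), so that it is clear whether patients can know their RIPC status.

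The cost is one extra form and wording changes in five sections, plus the reconciliation of the RIPC comparator. A few patients may need help marking the form soon after PCI, and a helper unaware of allocation may not always be at hand. No extra visits or patients are needed, and N stays at 152.

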11.2 Calculation or derivation of safety variable(s)

The frequency of bleeding according the TIMI criteria will be recorded.

12. STATISTICAL METHODS AND SAMPLE SIZE DETERMINATION

12.1 Description of analysis sets

All variables will be analyzed descriptively with appropriate statistical methods: categorical variables by frequency tables and continuous variables by sample statistics (i.e. mean, standard deviation, minimum, median, quartiles, and maximum).

Demographic variables and baseline characteristics will be summarized by treatment group for 2 analysis populations (i.e. valid for safety analysis and valid for per protocol analysis of primary efficacy endpoint). Medical history findings and adverse events will be coded by Medical Dictionary for Regulatory Activities (MedDRA) codes and medications by Anatomic Therapeutic Chemical Classification System (ATC) codes (World Health Organization-Drug Dictionary [WHO-DD]).

